4.2. Modified Intent-to-Treat (mITT)

All randomized subjects who receive at least one (1) dose of the IP will be included in the mITT population. The mITT will be the population used for the efficacy analyses. Subjects will be analyzed according to the treatment arm assigned at randomization, irrespective of compliance or any deviations in the study drug received. In addition, no subjects (or data) will be excluded due to protocol deviations that occur during the study.

4.3. Per-Protocol (PP)

The PP population will include all mITT subjects who meet all of the enrollment criteria and complete the efficacy evaluations at Day 29 without any major protocol deviations that have been deemed to affect the efficacy assessments. Significant deviations may include poor compliance, use of a prohibited concomitant drug, etc. The determination of all protocol deviations and any subjects excluded from the PP population will be made prior to locking the final database.

The PP population will be evaluated as a sensitivity analysis for the primary efficacy endpoint.

5. MISSING DATA

If a baseline value is missing, then the screening value will be carried forward and imputed to baseline if a screening value exists. If a baseline value is missing and there is more than one screening value, then the value taken on the date closest to the baseline date will be used.

For the SAF, mITT and PP populations, only observed data will be included and no outcome data will be imputed for missing values. This includes the primary and exploratory efficacy endpoints.

5.1. Conversion of Categorical Values

In some instances, continuous variables are expressed as a range (i.e., <10). In such cases, values may be converted to the range boundary (upper or lower limit as applicable). For example, a value of <10 may be converted to 10. Any adjustments made in this scenario will be clearly documented in the footnotes of relevant outputs.

6. GENERAL STUDY ASSESSMENTS

Study assessments and their schedules are presented in Section 2.3, Table 1. For more details on the assessments and procedures, please refer to the study protocol.

6.1. Disposition

Population: All Subjects

Subject disposition will include the following information, tabulated by treatment arm:

- Number and percentage of subjects who were:
 - Screened
 - Screen failed at Visit 1
 - Screen failed at Visit 2
 - Randomized
 - Treated
 - Withdrawn
 - Completed the study and completed each visit

Note: For the subjects treated with study drug, withdrawn, completing the study, and completing each visit, percentages will be calculated based on total number of subjects randomized.

- Populations outlined in Section 4 will be described by treatment arm, with percentages based on the total number randomized.
- Subjects who are withdrawn from the study and the reason for withdrawal will be tabulated and listed for all randomized subjects. Summaries will include the number and percentage of subjects within each treatment arm. Reasons will include the following:
 - A serious or intolerable AE
 - A clinically significant change in systemic health
 - Sponsor or Investigator terminated the study
 - Subject requested to be discontinued from the study
 - Other

6.2. Protocol Deviations

Population: All Randomized Subjects

Protocol deviations will be summarized and listed by treatment arm and deviation type (study visit window, study drug, etc.) for all randomized subjects. Out-of-window protocol deviations will be evaluated on a case-by-case basis.

6.3. Demographic and Baseline Information

Population: All Randomized Subjects

Demographic and baseline characteristics will be summarized by treatment arm. Demographic variables will include age, sex, race, ethnicity, and iris color.

Disease-specific baseline variables will include summaries at Day 1 of the SE for the following parameters:

- Unanesthetized Schirmer's Test
- Anesthetized Schirmer's Test
- VAS of IP Comfort (ASHRAE 7-Point Scale)
- VAS of Eye Dryness Score
- VAS of Ocular Discomfort Score
- SAnDE Scores (assessed OU)
- Inferior CFS Score
- Total CFS Score
- BCVA (LogMAR Score)
- IOP (mmHg)

Continuous variables will be summarized using descriptive statistics, including the n, mean, median, standard deviation, minimum and maximum. Categorical variables will be summarized using counts and percentages of subjects.

It is assumed that the randomization plan used in this study will minimize differences between treatment arms with respect to the demographic and baseline characteristics. Baseline comparability between treatment arms will be assessed via descriptive statistics.

6.4. Medical and Ocular History

Population: SAF

Significant, relevant medical history will be recorded at Screening.

All medical and ophthalmic histories reported at Screening will have their verbatim term mapped to their corresponding thesaurus terms using version 27.1 of the Medical Dictionary for Regulatory Activities (MedDRA®) coding dictionary. All summaries will be based on the assigned MedDRA Preferred Term (PT) and System Organ Class (SOC), and summaries will be provided by treatment arm. Separate summaries will be created for the medical (non-ocular) and ophthalmic histories. For ophthalmic histories, separate summaries will be created for the SEs and fellow eyes (FEs).

Results will be reported as subject incidence counts (number and percentage of subjects) within each PT and SOC. If a subject has more than one history that was coded to the same PT and SOC, then the subject will only be counted once for that PT and SOC.

6.5. Concomitant Medications

Population: SAF

All concomitant medications and procedures listed on the electronic case report form (eCRF)

will be provided in data listings.

Each medication will be mapped to its corresponding thesaurus terms (Anatomical-Therapeutic-Chemical [ATC] Class and Standardized Medication Name) from the January 2024 version of the World Health Organization (WHO) Drug Dictionary. A subject incidence count summary table (i.e., number and percentage of subjects) of all concomitant medications used during the study, sorted by ATC Class and Standardized Name, will be provided by treatment arm. For incidence count reporting, if a subject has more than one medication that is coded to the same Standardized Name and ATC Class, then the subject will only be counted once for that Standardized Name and ATC Class.

7. ANALYSIS OF ENDPOINTS

7.1. General Considerations

Summary statistics for the data collected during this study will be presented to give a general description of the subjects studied. Data from all sites will be combined in the computation of these descriptive summaries. Categorical variables will be summarized by the frequency and percentage of subjects in each category. Unless otherwise noted, the denominator to determine the percentage of subjects in each category will be based on the number of subjects with available data. When appropriate, comparisons on categorical data will be analyzed using the Cochran-Mantel-Haenszel or Fisher's exact test. Continuous variables will be summarized using N, mean, standard deviation (SD), median, minimum, and maximum values, and will be analyzed comparatively using the methodologies outlined under the primary and exploratory efficacy considerations (Sections 7.3 and 7.4) when appropriate.

For the descriptive statistics, minimum and maximum values will be calculated to the same number of decimal places as the source data. Means, medians and confidence limits will be calculated to one more decimal place than the source data. Standard deviations will be calculated to two more decimal places than the source data. Percentages will be calculated to the nearest one decimal place.

Unless otherwise specified or the parameter is evaluated OU, efficacy analyses will be performed on the SE only. Ocular safety summaries will be presented separately for the SE and the fellow eye (FE).

Efficacy variables will be summarized descriptively at each visit (where assessed) for both the SE and FE, and analyzed using appropriate statistical methods. The exam performed at Visit 2 (Day 1) will be used as baseline. If the assessment is missing or not evaluated on Day 1, the screening exam will be used, if available. Data from all clinical sites will be pooled so that the target sample size is available for analysis.

Treatment-group comparisons will include IVW-1001 Ophthalmic Wipe 0.2% vs. Vehicle and IVW-1001 Ophthalmic Wipe 0.1% vs. Vehicle for the primary and exploratory efficacy endpoints. Statistical tests will be presented as two-sided p-values rounded to four decimal places; p-values less than 0.0001 will be presented as '<0.0001' and p-values = 1 will be presented as '>0.999' in all tables. Efficacy analyses will be carried out using a two-sided, $\alpha = 0.05$ significance level without adjustments for multiplicity, as this is a Phase 1/2a study.

All data collected in this study will be presented in individual data listings for all subjects.

7.1.1. Efficacy Analyses Specific Considerations

For all efficacy parameters, descriptive statistics will be presented as outlined in Section 7.1. A basic statistical model assessment will be done for all parameters, where appropriate, including but not limited to, the Shapiro-Wilk test to confirm normality of the data, and residual assessment for independence, lack of fit, and equality of variance.

Departures from normality will be addressed by first assessing for multiple distributions in the data through the generation of histograms, and for potential outliers by boxplot creation. Outliers will be discarded if the values are deemed impossible for the assessment, or there is independent

evidence that the observation is incorrect and there is no information to correct the error. Other apparent outliers will be noted but not discarded. One of the following transformations, applied as appropriate, may be employed:

- If data are skewed, it will be transformed by a log or square root transformation
- If data is relatively normal with a few unexplained outliers, it will be analyzed with and without identified outliers as an ad-hoc sensitivity analysis
- If normalization cannot be achieved via transformation methods, non-parametric analysis methodology will be used

7.2. Primary Safety Endpoint Assessments and Analysis

The primary objectives for this study are to investigate the safety and tolerability of the IVW-1001 Ophthalmic Wipe based on the following safety endpoints:

- CFB in BCVA, slit lamp biomicroscopy, IOP and dilated ophthalmoscopy
- VAS of IP tolerability
- Adverse Events

Safety analyses will be performed on all subjects who received at least 1 dose of IP (SAF Population). The assessment of safety will be based on the summary of ocular and non-ocular AEs and ophthalmic/medical exams (BCVA, slit lamp biomicroscopy, IOP, dilated ophthalmoscopy and tolerability assessment). Summaries will be provided for each treatment arm, and for the ophthalmic exams, separately for SE and FE.

Safety variables will be presented descriptively. Continuous variables will be summarized by descriptive statistics (absolute values and changes from baseline), and categorical variables will be summarized using the count and percentage of subjects in each category. For the biomicroscopy and ophthalmoscopy variables, shift tables will be prepared by treatment arm showing all categorical changes (e.g., normal to abnormal) from baseline to each study visit.

All data will be presented in data listings.

7.2.1. Adverse Events

Population: SAF

An AE is the development of an undesirable medical condition or the deterioration of a preexisting medical condition during the study, whether considered causally related to the product or not. An AE can therefore be any unfavorable or unintended sign (including a clinically significant change in laboratory values or other clinical tests), symptom, or medical condition occurring at any time during or after IP administration.

Note: Any clinically significant findings (including a clinically significant change in laboratory values or other clinical tests) prior to study drug administration or at Screening (after informed consent) will be recorded in medical/ocular history.

Ongoing AEs at study completion or the subject's final study visit will be followed until the event resolves, stabilizes, or for 30 days, whichever comes first.

AEs reported during the study will have their verbatim terms mapped to the corresponding thesaurus terms from the most current version of the Medical Dictionary for Regulatory Activities (MedDRA®) coding dictionary, version 27.1. All summaries will be based on the assigned MedDRA Preferred Term and System Organ Class, and summaries will be given for each treatment arm. If a subject has more than one AE that is coded to the same PT and SOC, then the subject will only be counted once for that PT and SOC.

The following AE summaries will be prepared:

- Overall Summary of AEs
- Treatment-Emergent Adverse Events (TEAEs) by SOC and PT
- TEAEs by SOC, PT and Maximum Severity (mild, moderate, severe)
- Study Drug Related TEAEs by SOC and PT
- TEAEs Causing the IP to be Discontinued (listing only)
- All Serious Adverse Events (SAEs) (listing only)

7.2.1.1. Adverse Events Occurring During the Run-In Period

Adverse events will be collected throughout the entirety of the study, including during the run-in period. If an AE begins during the run-in period and continues into the treatment period, then the AE will also be counted as a treatment-period event.

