8 ADVERSE EVENTS

8.1 Definition of an Adverse Event

An AE is defined as any untoward medical occurrence in a subject regardless of its causal relationship to the IP. An AE can be any unfavorable and unintended sign (including any clinically significant laboratory test result), symptom, or disease temporally associated with the use of the IP, whether or not it is considered related to IP administration. Included in this definition is any newly occurring event or previous condition that has increased in severity or frequency since the administration of the IP.

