8.5 Recording of Adverse Events

All AEs should be reported starting after the first IP dose is administered (during the run-in period) and through 30 days after last dose of IP. The Sponsor may request follow-up on any unresolved AEs within 30 days after the final study visit.

All conditions present prior to receiving the IP should be documented as medical history. Information to be collected includes type of event, date of onset, date of resolution, and Investigator-specified assessment of severity and relationship to the IP.

While an AE is ongoing, changes in the severity (eg, worsening and improving) should be noted in the source documents but, when documenting the AE, only the total duration and greatest severity should be recorded in the electronic case report form (eCRF). Adverse events characterized as intermittent require documentation of onset and duration.

Pre-existing conditions (present before the start of the AE collection period) are considered concurrent medical conditions and should NOT be recorded as AEs. If the subject, however, experiences a worsening or complication of such a concurrent condition, the worsening or complication should be recorded as an AE. The Investigator should ensure that the AE term recorded captures the change in the condition (eg, ‘worsening of’).

Each AE should be recorded as a single diagnosis. Accompanying signs (including abnormal laboratory test values) or symptoms should NOT be recorded as additional AEs. Changes in laboratory test values are only considered to be AEs if they are judged to be clinically significant (ie, if some action or intervention is required or if the Investigator judges the change to be beyond the range of normal physiological fluctuation). If abnormal laboratory test values are the result of pathology for which there is an overall diagnosis (eg, increased creatinine in renal failure), only the diagnosis should be reported as an AE.

Pre-planned elective procedures (surgeries or therapies) known at the time of randomization that are performed to manage/treat conditions that existed prior to the subjects’ enrolling in the study (eg, elective periodontal surgery, elective hernia repair) should not be recorded as AEs but should be documented in the subject’s source documents. If a pre-planned procedure is performed early (eg, as an emergency) because the pre-existing condition worsens, the worsening condition should be captured as an AE.

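### SAP 7.2.1.1 counts an adverse event that began on run-in vehicle and merely persists past Day 1 as a treatment-period event, and neither document defines a treatment-emergent event or its reference dose.

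*SAP*

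**What the plan says.** Protocol 6.1 puts every subject on vehicle during the run-in; SAP 2.2 starts the treatment period on Day 1, with the first assigned dose. Protocol 8.5 starts AE collection at the first IP dose and states that this falls in the run-in. Protocol 7.5.1 also calls the run-in vehicle IP.

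SAP 7.2.1.1 collects AEs throughout. If an AE begins in the run-in and "continues into the treatment period, then the AE will also be counted as a treatment-period event". Persistence is the only condition. The word 'also' means that the event counts in both periods.

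SAP 7.2.1 then builds three tables and one listing on TEAEs. They include "TEAEs by SOC, PT and Maximum Severity (mild, moderate, severe" and "Study Drug Related TEAEs by SOC and PT", and "summaries will be given for each treatment arm". The abbreviation list only expands the term TEAE, and the protocol does not use it. SAP 2.3.1 numbers study days from the first study drug administration, but that is a day-numbering convention and sets no rule for emergence.

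On recording, protocol 8.5 says that, when an AE is documented, "only the total duration and greatest severity should be recorded in the electronic case report form (eCRF". Changes in severity are noted in source documents.

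**The concern.** Safety and tolerability are the stated primary objectives (SAP 7.2), and the AE tables by arm are the main way they are reported. A reader will take a treatment-emergent table to show what began or worsened on the randomized product. Under the rule as written it can also show events that began before any active product was used and never changed.

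Two recording conventions make this hard to undo from the tables. First, the eCRF holds one greatest severity per AE, so a peak reached on run-in vehicle can appear as the maximum severity under an active arm. Second, the instruction that "the worsening or complication should be recorded as an AE" is given for conditions described as follows: "Pre-existing conditions (present before the start of the AE collection period". Collection begins in the run-in, so an AE that starts there is not pre-existing in that sense, and its later worsening need not become a new record. In the database, an event that persisted unchanged and one that worsened on randomized product can then look the same.

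Relatedness is judged against IP (protocol 8.3), and run-in vehicle is IP. A judgement made about run-in vehicle can therefore reach the drug-related table.

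**Working it through.** The documents state no run-in AE rate and no figure that depends on this rule, so there is nothing to reproduce. The text settles the rule; the arithmetic below only gives its likely size.

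**Text.** Under SAP 7.2.1.1 the conditions for a treatment-period count are onset in run-in and continuation past Day 1. No sentence in either document adds an increase in severity or frequency after Day 1. No sentence says whether emergence is measured from the first IP dose (run-in vehicle) or the first randomized dose. If it were the first IP dose, AEs that both began and ended in run-in would qualify too.

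**Inputs from the documents.** Run-in 7 days, treatment 28 days, 50 subjects per arm.

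**Assumptions, not in the documents.** AE risk over 28 days of 10% on vehicle and 25% on active; constant vehicle hazard across run-in and treatment; a share s of run-in events still ongoing at Day 1; independence of run-in and on-treatment events.

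**Formulas.** Carry-over c = [1 − (1 − p_vehicle)^(7/28)] × s. Displayed risk = 1 − (1 − p)(1 − c). Expected carried-over subjects per arm = 50c. Chance of at least one in the two active arms = 1 − (1 − c)^100. Chance that two arms differ by 3 or more carried-over subjects comes from two independent Binomial(50, c) counts.

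With s = 1, c = 1 − 0.90^0.25 = 0.0260. Displayed vehicle risk is 1 − 0.90 × 0.9740 = 0.1234, and displayed active risk is 1 − 0.75 × 0.9740 = 0.2695.

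| s | c | Subjects per arm of 50 | Displayed risks | Ratio (true 2.50) | Difference (true 15.0 points) | At least 1 in active arms | Arms differ by 3 or more |
|---|---|---|---|---|---|---|---|
| 1 | 0.0260 | 1.30 | 12.3% v 27.0% | 2.18 | 14.6 | 0.93 | 0.11 |
| 0.5 | 0.0130 | 0.65 | 11.2% v 26.0% | 2.33 | 14.8 | 0.73 | 0.03 |
| 0.25 | 0.0065 | 0.32 | 10.6% v 25.5% | 2.41 | 14.9 | 0.48 | 0.006 |
| 0.1 | 0.0026 | 0.13 | 10.2% v 25.2% | 2.46 | 15.0 | 0.23 | 0.0006 |

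For a single preferred term at 2% v 10%, full persistence gives c = 0.0050 and displayed risks of 2.5% v 10.5%. The difference stays at 8.0 points, and the chance of at least one carried-over subject in the active arms is 0.40 (0.22 at s = 0.5).

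If the run-in hazard were twice the on-treatment hazard with full persistence (10% v 25% case), c = 1 − 0.90^0.5 = 0.0513, the ratio is 1.97 and the difference 14.2 points.

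**The case against.** **The rule over-counts, which is a defensible choice for safety.** It cannot miss a run-in AE that worsened on drug, whereas a worsening-only rule can, given that the eCRF keeps one severity. This stands, and the fix has to provide for it.

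**The link to the TEAE tables is inferred.** The SAP says treatment-period event, not TEAE, and lists an overall AE summary separately. On a narrow reading the rule touches only that summary, and the maximum-severity and drug-related consequences fall away. This is possible, but the plan would then have no rule at all for TEAEs, so SAP text is needed either way.

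**Attribution to the arm is not plainly wrong.** The active wipes share the vehicle's other ingredients and the wiping procedure. This is fair for cause, but it does not help a reader who wants to see what the active ingredient adds.

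**Carry-over may be low.** Protocol 4.3 re-checks eligibility at Baseline: grade 4 staining, IOP of 23 mmHg or more, suspected infection and ocular inflammation not related to DED all exclude. Subjects with such events ongoing should not be randomized. This stands, and it is a reason not to lean on the full-persistence row.

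**A stronger reading to avoid.** A reader might infer that protocol 8.1 sets a stricter test that SAP 7.2.1.1 breaks, because 8.1 includes "any newly occurring event or previous condition that has increased in severity or frequency since the administration of the IP". It does not. That sentence defines an AE, not a TEAE, and its anchor is any IP, which includes run-in vehicle. An AE that begins in run-in meets it as newly occurring, so the two passages do not contradict each other.

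**Conclusion.** The point holds with a modest size. As written, the plan lets persistence alone turn a vehicle-onset event into a treatment-period event, and it leaves TEAE and its reference dose undefined. The harm is misattribution of individual events, and of severity or relatedness calls from run-in, to an arm, plus slightly raised rates in every arm.

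A reader might infer that the rule biases the comparison of active with vehicle. The documents do not support that. Run-in precedes randomization, so carried-over events are balanced in expectation. Safety is summarized descriptively with no test planned, and the risk difference falls by at most 0.4 points in the table above. SAEs and events that stop the IP are listed, and listings of all data keep onset dates traceable. What remains is that the summary tables themselves would not show the carry-over.

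The range of 0.1 to 1.3 subjects per arm rests on an assumed 10% vehicle rate, a constant hazard and assumed persistence between 0.1 and 1. The figure of 0.93 for at least one such subject in the active arms is the value at full persistence, not an estimate.

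**What to change.** - In SAP 7.2.1, define a TEAE as an AE with onset, or worsening of a run-in AE, on or after the first dose of randomized IP on Day 1.
- Replace the carry-over sentence in SAP 7.2.1.1 with that definition.
- State that the severity tabulated is the one reached on or after that dose.
- Tabulate run-in AEs in a separate table.
- For run-in AEs ongoing at Day 1, establish worsening by a source check or by a separate worsening entry in the eCRF.
- Where worsening cannot be determined, keep the event in the TEAE tables and flag it as run-in onset, so that on-drug worsening is not missed.

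**Cost.** The SAP wording and one extra table are cheap. The source check covers few subjects. It relies on protocol 8.5, which has severity changes noted in source but does not say that they are dated. A separate worsening entry goes beyond SAP wording: it extends the convention in protocol 8.5 and changes eCRF practice.
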